#### 8.1.3. Cohort 3 Plasma Collection

WB-derived plasma will not be used in Cohort 3 due to safety concerns regarding the number of donations required to collect the volume of plasma needed to manufacture 3 units (approximately 810 mL) of FDP and 3 units (approximately 810 mL) of FFP. All subjects in Cohort 3 will undergo plasmapheresis collection. Cohort 3 subjects will be randomized no more than 48 hours prior to the first infusion to 1 of 2 treatment arms that will be based on the order of the products received. Subjects in Treatment Arm 5 will receive a 3 unit (approximately 810 mL) transfusion of FDP followed by a 3 unit (approximately 810 mL) transfusion of FFP. Subjects in Treatment Arm 6 will receive a 3 unit (approximately 810 mL) transfusion of FFP followed by a 3 unit (approximately 810 mL) transfusion of FDP. Subjects will be blinded to their treatment order assignments.

During the Collection Visits, all Cohort 3 subjects will:

• Be asked to provide information about medical history, concomitant medications, and AEs since the screening visit;

- Undergo an abbreviated physical exam which includes vital signs (blood pressure, heart rate, respiration rate, and temperature) and a general assessment of health;
- Complete the AABB Donor History Questionnaire;
- Provide a sample of blood for hematocrit testing prior to (each) donation per the SOPs in place at the site; and
- Provide a plasma donation by plasmapheresis in compliance with the clinical site's SOPs regarding plasmapheresis donation.

Cohort 3 subjects will need to make 2 to 3 plasmapheresis donations (up to 800 mL per collection) that will be scheduled to take place, minimally, a week apart. Post-donation, subjects will be monitored for any adverse effects associated with plasmapheresis donation (see section 5.6.1.3). The SPEP will be routinely performed at as part of all Cohort 3 collection visits. Should the SPEP results reveal the subject as ineligible for their current plasmapheresis, the subject may be rescheduled to return in no less than 7 days. Just prior to Cohort 3 subjects' second or subsequent plasmapheresis donation at each plasmapheresis collection, a SPEP test will be performed. After the first plasmapheresis collection, a STAT Total Protein will be performed as a condition of initiating plasmapheresis at subsequent collection visits. Post-donation, all subjects will be monitored for any adverse effects associated with plasmapheresis donation (see section 5.6.1.3).

Approximately 10% of plasma units that are supplied for manufacturing of FDP are damaged during the process. Those units must be discarded and cannot be infused. If that happens to a subject's plasma unit, they will be asked to return to the clinic for additional plasmapheresis collections in order to meet the total required volume for the manufacturing of 1,620 mL of plasma.

Subjects who do not meet the study's minimum collection volume requirements of 500 mL during plasmapheresis may be withdrawn from the study. The low volume donation collections (< 500 mL) will be discarded per the clinical site's SOP for handling blood and blood products.

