#### **Estimated Number of Subjects to Screen: 48**

#### Maximum Number of Subjects to Enroll: 24

Cohort 1, Arm 1: (n=4) subjects are to be infused with 1 autologous FDP unit (FDP-CPD) manufactured from WB-derived FFP.

Cohort 1, Arm 2: (n=4) subjects are to be infused with 1 autologous FDP unit (FDP-ACD) manufactured from FFP collected via plasmapheresis.

Cohort 2. Arm 3: (n=4) subjects are to be infused with 2 autologous FDP (FDP-CPD) units manufactured from WB-derived FFP.

Cohort 2, Arm 4: (n=4) subjects are to be infused with 2 autologous FDP units (FDP-ACD) manufactured from FFP collected via plasmapheresis.

Both arms of Cohort 3 are to be infused with 3 units of autologous plasma product at each of 2 infusion visits. Infusion visits are to be scheduled such that there is a period of no less than 2 weeks between infusions.

Cohort 3, Arm 5: (n=4) subjects will receive 3 autologous FDP units (FDP-ACD) manufactured from FFP collected via plasmapheresis at their first infusion visit followed by infusion with 3 autologous FFP units, collected via plasmapheresis, at their second visit.

Cohort 3, Arm 6: (n=4) subjects will be infused with these products in the opposite order as Arm 5 (eg, autologous FFP at first infusion and autologous FDP-ACD at the second).

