# 5.7. Route of Administration, Dosage Regimen, Treatment Period, and Justification

In this safety study, 3 cohorts of healthy subjects will receive an intravenous (IV) infusion of FDP and/or FFP as follows:

- **Cohort 1:** Eight enrolled subjects will each receive a 1 unit (approximately 270 mL) dose of FDP:
  - Arm 1 subjects will receive 1 unit (approximately 270 mL) of autologous FDP manufactured from WB. These subjects are expected to make one WB donation. Subjects with a low-volume donation (< 450 mL) may be withdrawn from the study. The site will discard the low-volume donation per their SOP for handling blood and blood products.

  - Arm 2 subjects will receive 1 unit (approximately 270 mL) of autologous FDP manufactured from plasmapheresis collected FFP. These subjects are expected to undergo one plasmapheresis session. Subjects with a low volume donation (< 500 mL) may be withdrawn from the study. The site will discard the low-volume donation per their SOP for handling blood and blood products.

- Cohort 2: Eight enrolled subjects will each receive 2 units (approximately 540 mL) of FDP:
  - Arm 3 subjects will receive 2 units (approximately 540 mL) of autologous FDP manufactured from WB. These subjects are expected to make two WB donations that are scheduled a minimum of 28-days apart. Subjects with a low-volume donation (< 450 mL) may be withdrawn from the study. The site will discard the low-volume donation per their SOP for handling blood and blood products.

  - Arm 4 subjects will receive 2 units (approximately 540 mL) of autologous FDP manufactured from plasmapheresis collected FFP. These subjects are expected to undergo one plasmapheresis session. Subjects with a low-volume donation (< 500 mL) may be withdrawn from the study. The site will discard the low-volume donation per their SOP for handling blood and blood products.
    - Should an Arm 4 subject require a second plasmapheresis collection attempt, to ensure subject safety, serum protein electrophoresis (SPEP) and STAT total protein will be performed just prior to the subsequent plasmapheresis. If any abnormalities are detected, the subject will be referred to a physician, scheduled for early withdrawal, and replaced with another subject.

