- Cohort 3: Eight subjects will each receive 2 separate infusion treatments, each dosed at approximately 810 mL. One 810 mL infusion will be with 3 units of autologous FDP and the other approximately 810 mL infusion will be with 3 units of autologous control plasma (FFP). Cohort 3 subjects will be randomized to a product treatment sequence indicating whether their first infusion will be FDP (Arm 5) or FFP (Arm 6).

The starting material for the manufacture of all Cohort 3 FDP units and FFP units will be from autologous plasmapheresis.

- Arm 5 subjects will receive FDP at their first infusion and FFP at their second infusion; infusion treatments will be separated by a 2-week interval; and
- Arm 6 subjects will receive FFP at their first infusion and FDP at their second infusion; infusion treatments will be separated by a 2-week interval.

All subjects in Cohort 3 are expected to undergo 3 to 4 plasmapheresis sessions that are each separated by a minimum of 1 week. Subjects who do not meet the minimum volume requirement during plasmapheresis (≥500 mL) may be withdrawn from the study. Low volume collections (< 500 mL) will be discarded per the clinical site's SOP for handling blood and blood products.

As a measure of donor safety, SPEP will be performed on all subjects undergoing the procedure, regardless of assigned cohort/treatment arm. If any abnormalities are detected, the subject will be referred to a physician, scheduled for early withdrawal, and replaced with another subject.

For subjects undergoing multiple plasmapheresis collections, total protein measured by a Beckman Coulter AU analyzer will be performed STAT or up to 24 hours prior to initiating the plasmapheresis. Total protein will only be performed at subsequent plasmapheresis sessions, not during the first collection.

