<sup>HMonitor vital signs every 15 minutes during infusion; every 30 minutes for up to 4 hours post-infusion; and after 6 hours, vital signs should be measured every 4 hours until the subject is released. Subjects assessed for DVT, PE, and cardiac ischemia using the Wells Scale prior to infusion, at 30 minutes, 4 hours, and 24 hours post-infusion before the subject can be released from the clinic.

<sup>1Chemistry panel includes Calcium, ALP, ALT, AST, Bicarbonate, Chloride, Glucose, Potassium, Sodium, Total Bilirubin, Total Protein, BUN, Lactate, and Creatinine. pH, Ionized Calcium and Total Magnesium will only be measured at pre-infusion and 0.5 hour post-infusion.

<sup>JSee Table 9 - Laboratory Testing Schedule and Volumes for Cohort 3 for sampling time points.

KCBC comprises Hematocrit, Hemoglobin, Platelet Count, RBC Count, and WBC Count.

<sup>LSPEP is performed on the donated plasma at each plasmapheresis visit.

MCoagulation testing for Factors I, II, V, VII, VIII, IX, X, XI von Willebrand Factor activity, and Total Protein C and S activity.

N Follow-up phone calls to the subject will be made 48 hours and 72 hours following both Infusion Visits. The 14-day follow-up phone call will only occur after Infusion Visit #2.

<sup>o Total Protein can be performed up to 24 hours prior to each subsequent plasmapheresis session.

PAdditional collection visits may be required in the event that a plasma unit experiences an issue during preparation (eg, leakage during transfer to lyophilization bag) or during lyophilization (eg, bag breakage during freeze-drying).

O These tests are for research purposes only and will not be used to manage the safety of study participants.

Table 9: Laboratory Testing Schedule and Volumes for Cohort 3

Laboratory and Coagulation Factor Testing	Screening	Collection Visits		fusion Visit #1 and #2	ts	24-Hour Follow-Up	7-Day Follow-Up	28-Day Follow-Up
			Pre-	Post-I	nfusion	Visits	Visits	Visit
			Infusion	0.5 hr	4 hrs			
Pregnancy Test (females only)	X		X					
Urine Drug Screening	X							
Urinalysis	X		X	X	X	X		
Chemistry Panel A	X		X	X	X	X	X	
CBC B	X		X	X	X	X	X	X
Hematocrit		X						
PT/INR	X		X	X	X	X		X
aPTT	X		X	X	X	X		X
DAT (IgG and C3)	X		X			X		X
Blood Type for ABO and Rh	X		Xc					
Red-Cell Antibody Screen	X							
Syphilis Screen	X							
HTLV Antibody Screening Test	X							

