### 8. TREATMENT OF SUBJECTS

#### 8.1. Whole Blood and Plasma Collection

The purposeful use of plasmapheresis in this study, particularly for Cohort 3 subjects, provides practical advantages to subjects (eg, fewer required collection visits) and minimizes potential issues related to subject safety. WB donations generally provide a net volume of approximately 250 mL of derived plasma and typically require a 56-day interval between donations. In this study, subjects who are required to make more than one autologous WB donation (eg, subjects in Cohort 2, Arm 3), the donation interval will be abbreviated to 28 days. Plasmapheresis collections, in contrast, have a much shorter 7- to 10- day donation interval since there is minimal loss of red blood cells (RBCs) during the process. The volume that can be collected during single plasmapheresis is  $\leq 800$  mL, depending on the donor's size, which is over twice the plasma volume derived from WB donation. Limiting enrollment of subjects to those who weigh  $\geq$ 140 lbs and  $\leq$  220 lbs will help ensure each autologous plasmapheresis yields 600 mL to 800 mL plasma based on established volume limits for automated plasma collection (FDA-1992). Regardless of cohort or treatment arm, all subjects will have SPEP performed at each plasmapheresis collection. If any abnormalities are detected, subjects will be referred to a physician, scheduled for early withdrawal, and replaced with another subject. For subjects undergoing multiple plasmapheresis collections, total protein will be performed STAT or up to 24 hours prior to initiating the plasmapheresis. Total protein will only be performed at subsequent plasmapheresis sessions, not during the first collection. All subjects regardless of cohort or treatment arm will be provided with information and instructions regarding the use of iron supplements (see Appendix G) during the donation period.

Following standard blood product SOPs, subjects' plasma products collected, manufactured, and prepared for autologous infusion will be visually examined. The visual inspection of both FFP and reconstituted FDP will include observation for signs of lipemia, hemolysis, clotting, and macroscopic particulate matter. Plasma units that do not meet the visual examination criteria will be discarded per the site's SOP for the destruction of blood and blood products.

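### Section 8.1.3 lets a Cohort 3 donor with a disqualifying SPEP be rescheduled, while sections 5.7 and 8.1 require withdrawal and replacement for any SPEP abnormality in any cohort

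*Protocol*

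**What the plan says.** Section 5.7 gives the general rule after the Cohort 3 description: "As a measure of donor safety, SPEP will be performed on all subjects undergoing the procedure, regardless of assigned cohort/treatment arm". The consequence follows at once: "If any abnormalities are detected, the subject will be referred to a physician, scheduled for early withdrawal, and replaced with another subject". The Arm 4 bullet in the same section attaches the same consequence to a repeat collection, where "serum protein electrophoresis (SPEP) and STAT total protein will be performed just prior to the subsequent plasmapheresis".

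Section 8.1, the parent of the three cohort-specific collection sections, requires SPEP at every plasmapheresis collection in every cohort and arm, and repeats the consequence: "If any abnormalities are detected, subjects will be referred to a physician, scheduled for early withdrawal, and replaced with another subject".

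Section 8.1.3 covers Cohort 3. SPEP is part of every collection visit, and for repeat sessions "Just prior to Cohort 3 subjects' second or subsequent plasmapheresis donation at each plasmapheresis collection, a SPEP test will be performed". On an adverse result it says: "Should the SPEP results reveal the subject as ineligible for their current plasmapheresis, the subject may be rescheduled", to come back after at least 7 days. It mentions neither referral nor withdrawal nor replacement.

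Table 8 footnote L, also for Cohort 3, says "SPEP is performed on the donated plasma at each plasmapheresis visit".

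The SAP lists SPEP results with an abnormal flag (Listing 31) but sets no handling rule.

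**The concern.** One event, a disqualifying SPEP at a Cohort 3 collection visit, has two consequences in the protocol. Under 5.7 and 8.1 the donor must leave the study and be replaced. Under 8.1.3 the same donor may return about a week later.

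The protocol presents SPEP as a donor-safety check, and the looser rule sits in the cohort that donates most. Section 5.7 and Table 3 give 3 to 4 sessions for Cohort 3, against one expected for Arms 2 and 4. These are healthy volunteers with no expected benefit.

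There is also a practical consequence. The same handling is compliant under one section and a deviation under another. Section 14.1.3 requires deviations to be documented, and SAP Listing 37 reports them. Listing 31 will flag the abnormal result, so any such case will be visible to an inspector.

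**Working it through.** The protocol states no figure on this point, so the check is a comparison of the texts.

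| Section | Applies to | Trigger | Consequence | Force |
|---|---|---|---|---|
| 5.7, Arm 4 bullet | Arm 4, repeat session | any abnormality at the pre-session check | referral, withdrawal, replacement | mandatory |
| 5.7, all-subject paragraph | every plasmapheresis subject | any abnormality | referral, withdrawal, replacement | mandatory |
| 8.1 | every plasmapheresis subject, each collection | any abnormality | referral, withdrawal, replacement | mandatory |
| 8.1.3 | Cohort 3 | SPEP makes the subject ineligible for the current session | return after at least 7 days | permitted |

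1. *Does the trigger separate the rules?* No. An SPEP result that disqualifies a donor falls within any abnormality on an ordinary reading, and the protocol defines no narrower class.
2. *Does the cohort separate them?* No. Both 5.7 and 8.1 apply regardless of cohort and arm, and 8.1.3 claims no exemption.
3. *Does timing separate them?* No. Section 8.1.3 takes the SPEP before second and later sessions, and the Arm 4 bullet attaches withdrawal to a check at that same point.
4. *Can both be obeyed?* Only if the site never uses the rescheduling option. Using it breaches 5.7 and 8.1.
5. *Footnote L.* A test on donated plasma cannot serve as a check before the donation. It therefore conflicts with 8.1.3 for second and later visits. It does not conflict for the first visit, where 8.1.3 says only that SPEP is part of the visit. Section 8.1.2 likewise describes Arm 4's SPEP as measured during donation.

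**Size for one affected donor at the last session.** Inputs are the synopsis duration table (screening about 2 weeks, Cohort 3 collection about 3, manufacturing about 5) and the 7-day minimum deferral.

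- Deferral: 1 + 5 = 6 weeks to first infusion.
- Replacement: 2 + 3 + 5 = 10 weeks.
- Difference: 10 − 6 = 4 weeks.

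**Plasma already given by a donor withdrawn at the last session**, at 500 to 800 mL per accepted donation:

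- With 3 to 4 sessions (5.7, Table 3), there are 2 to 3 earlier donations: 2 × 500 = 1,000 mL to 3 × 800 = 2,400 mL.
- With the 2 to 3 donations that 8.1.3 itself states, there are 1 to 2 earlier donations: 1 × 500 = 500 mL to 2 × 800 = 1,600 mL.

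The higher session count is more plausible, since 2 × 800 = 1,600 mL falls short of the 1,620 mL required.

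**The case against.** The best defence is that 8.1.3 grants a permission. A site that refers, withdraws and replaces every such donor complies with all the sections. That stands, and it limits the problem to sites that use the option. It does not remove the conflict, because the protocol offers an option that its own general rule forbids.

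A second defence is that being ineligible for the current session suggests a passing finding, milder than an abnormality. The wording leans that way, but the protocol never draws the distinction, and the general rule covers any abnormality. The Manual of Procedures and the site's SOPs were not available and may contain a criterion. The protocol sections would still disagree.

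A third is that the donor remains protected. This largely stands. The disqualified session does not go ahead, SPEP is repeated at the next visit, STAT total protein is a condition of starting any session after the first collection, and section 7.6 lets the PI withdraw a subject for safety.

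A reader might infer that 8.1.3 sends the donor back without referral. The text does not support that: it is silent, and the referral duty in its parent section 8.1 can be read as still applying. A reader might also infer a breach of the synopsis ceiling, "Maximum Number of Subjects to Enroll: 24". That tension arises with any replacement, and section 6.6.1 provides for over-enrolment in the Cohort 3 randomization list, so it does not measure this conflict.

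**Conclusion.** The inconsistency is real and minor. Sections 5.7 and 8.1 mandate withdrawal and replacement where 8.1.3 permits rescheduling, and nothing in the protocol or SAP reconciles them. For a donor affected at the last session, the two routes differ by about 4 weeks to first infusion. That figure rests on the synopsis's approximate durations, the minimum deferral, and a replacement whose screening has not yet begun. The documents give no rate of abnormal SPEP, so the expected number of affected donors cannot be stated.

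It would be wrong to infer that the trial's safety conclusions are at risk. Cohort 3 randomization takes place no more than 48 hours before the first infusion, after collection. A donor withdrawn during collection remains in the all-enrolled population (F1), as the SAP defines it, and does not enter S1 to S3. Endpoints, the crossover comparison and conclusions on treatment-emergent adverse events are unaffected.

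**What to change.** In 8.1.3, delete the rescheduling sentence and put in its place: *If any SPEP abnormality is detected, the rule in section 8.1 applies (physician referral, early withdrawal and replacement).*

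If the sponsor and PI want to keep deferral, 8.1.3 should name the SPEP findings that allow it and require physician referral before the donor returns. Sections 5.7 and 8.1 should then carry a matching exception limited to Cohort 3. The rule for Arms 2 and 4 should stay as it is, since no conflict exists there.

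Align Table 8 footnote L with the pre-session sample required at second and later visits. Leave the existing SPEP and total protein checks in place.

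The preferred route costs one sentence and one footnote, with the approvals that section 14.1.2 requires for any modification. Its downside is a possible additional Cohort 3 replacement when a donor has an abnormal SPEP. Keeping deferral needs a clinical decision and, if it could increase risk to subjects, submission to the ORP and FDA before use. Neither route changes the sample size, the analysis or the visit schedule.

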#### 8.2. Plasma Infusion

### 8.2.1. Cohorts 1 and 2 Plasma Infusion

Prior to plasma infusion of subjects' in Cohorts 1 and 2, the following activities and procedures must be completed:

- Review of medical history, concomitant medications, and AEs since the collection visit(s);
- Conduct a complete physical examination that includes measurement of, body weight, and vital signs (blood pressure, heart rate, respiration rate, and temperature), and evaluation of cardiopulmonary systems, basic neurological function, and presence of DVT, cardiac ischemia, or PE. DVT will be assessed in conjunction with a subjects' D-Dimer test results and Wells scale score.(Dupras et al-2013);
- Collect urine and blood samples as noted for all tests listed in the Schedule of Events tables (Table 4, Table 5, and Table 6);

- Cross-match subject's RBCs to FDP; and
- Reverse ABO type on FDP.

At the discretion of the PI, a study plasma infusion may not be given if, in the PI's opinion, the subject's clinical status precludes a study plasma infusion and the planned protocol assessments. The reason for the PI's decision to withhold a study plasma infusion will be documented in the source documents and eCRFs. This does not preclude a standard of care plasma infusion.

After reconstitution of the FDP, a visual examination for signs of lipemia, hemolysis, clotting, or other issues that impact the quality and acceptability of the plasma for re-infusion will be performed. This visual inspection of FDP also includes observation of macroscopic particulate matter. Reconstituted FDP that does not meet visual examination criteria will be discarded per the site's SOP for the destruction of blood and blood products.

The date, start, and stop times of each plasma infusion will be recorded in the source document and eCRF. The scheduled dose of FDP will be transfused into subjects using a standard plasma administration set according to the clinical site's SOPs. The plasma product will be pumped into the vein at an initial rate of approximately 2-3 mL/minute for the first 10 minutes, and then the rate will be adjusted to not more than 10 mL/minute until completion of the plasma infusion. During the course of the infusion, vital signs (blood pressure, heart rate, respiration rate, and temperature) for all subjects will be monitored every 15 minutes (± 5 minutes) until the transfusion is completed.

Subjects will be observed during and after the study plasma infusion for evidence of acute transfusion reactions including: allergic reactions, bradycardia, tachycardia, or other cardiac dysrhythmia, hypertension, hypotension, dyspnea, hemolysis, fever, chills, thromboembolic events, bleeding, and infection. Subjects will remain at the study site under direct observation and actively monitored for a minimum of 5 to 6 hours post-infusion.

Vitals will be measured every 30 minutes ( $\pm$  5 minutes) up to 4 hours post-infusion and then once every 4 hours ( $\pm$  40 minutes) until the subject is released. The following laboratory tests will be performed at 30 minutes ( $\pm$  5 minutes) and at 4 hours ( $\pm$  40 minutes) post-infusion (see Table 7):

- Urinalysis;
- CBC (Hematocrit, Hemoglobin, Platelet Count, RBC Count, WBC Count);
- Chemistry panel (pH, Ionized Calcium and Total Magnesium [at 30 minutes post-infusion only], ALP, ALT, AST, Calcium, bicarbonate, lactate, Chloride, Glucose, Potassium, Sodium, Total Bilirubin, Total Protein, BUN, and Creatinine);
- PT/INR and aPTT; and
- D-dimer testing.

Prior to release, subjects will undergo an additional physical evaluation (eg, focus on cardiopulmonary systems, basic neurological function, and presence of DVT). The investigator will interpret exam findings in conjunction with the subjects' 4-hour post-infusion D-dimer test results and Wells criteria to determine the medical suitability for release.

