The date, start, and stop times of each plasma infusion will be recorded in the source document and eCRF. The scheduled dose of FDP or FFP will be transfused into subjects using a standard plasma administration set according to the clinical site's SOPs. The plasma product will be pumped into the vein at an initial rate of approximately 2-3 mL/minute for the first 10 minutes, and then the rate will be adjusted to not more than 10 mL/minute until completion of the plasma infusion. During the course of the infusion, vital signs (blood pressure, heart rate, respiration rate, and temperature) for all subjects will be monitored every 15 minutes (± 5 minutes) until the infusion is completed.

Subjects will remain at the study site and be actively monitored under direct observation for a minimum of 5 to 6 hours post-infusion. They will be asked about and observed during and after the study plasma infusion for evidence of acute transfusion reactions including: allergic reactions, bradycardia, tachycardia, or other cardiac dysrhythmia, hypertension, hypotension, dyspnea, hemolysis, fever, chills, thromboembolic events, bleeding, and infection.

Vitals will be measured every 30 minutes ( $\pm$  5 minutes) up to 4 hours post-infusion. Measurement of vitals will then be decreased to every 4 hours ( $\pm$  40 minutes) until the subject is released. The following laboratory tests will be performed at 30 minutes ( $\pm$  5 minutes) and at 4 hours ( $\pm$  40 minutes) post-infusion (see Table 9):

- Urinalysis;
- CBC (Hematocrit, Hemoglobin, Platelet Count, RBC Count, WBC Count);
- Chemistry panel (pH, Ionized Calcium and Total Magnesium [at 30 minutest post-infusion only], ALP, ALT, AST, Calcium, Bicarbonate, lactate, Chloride, Glucose, Potassium, Sodium, Total Bilirubin, Total Protein, BUN, and Creatinine);
- PT/INR and aPTT;
- DAT (IgG and C3);
- Coagulation factor tests (Factors I, II, V, VII, VIII, IX, X, XI, D-Dimer, von Willebrand Factor activity, Protein C activity, and Protein S activity); and
- PF 1+2, TAT, AT-III, Alpha-2 Antiplasmin, and C3a des Arg at 30 minutes post-infusion only. These tests are for research purposes only and will not be used to assess subject safety.

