## 10.5.1. Methods and Timing for Assessing, Recording, and Analyzing Adverse Events

All AEs will be assessed at all study visits, documented in the source records, and recorded on the eCRFs using accepted medical terms and/or the diagnoses that accurately characterize the event. When a diagnosis is known, the AE term recorded on the eCRF will be the diagnosis rather than a constellation of symptoms. The PI will assess and record for all AEs/SAEs: a description of the event (if the event consists of a cluster of signs and symptoms, a diagnosis should be recorded rather than each sign and symptom); onset date and time, and stop date and time; intensity (recorded as mild, moderate or severe); seriousness; causality (relationship to study drug); outcome (eg, resolved, resolved with sequelae, not resolved, fatal, or unknown if applicable); action taken with the study agent (eg, no action, study agent discontinued and other action taken).

When an event is not resolved by study closure, it will be documented on the AE eCRF as ""not recovered/not resolved".

AEs will be assessed using an open-ended question such as: "How have you been feeling since we last spoke?" If an AE that requires medical attention is reported to a nurse, it should be reported to a study physician immediately. The PI or study physician will assess subjects for any medical side effects, through a focused review of systems and physical exam. Specifically, they will be looking for evidence of coagulation disturbances. Subjects with suspected positive findings will be referred to their treating physicians for clinically indicated and appropriate evaluation and management. Acute plasma infusion reactions will also be specifically documented as follows:

- Fever (by oral or axillary temperature);
- Allergic reactions (i.e., skin rash; urticarial; pruritus; generalized flushing; localized angioedema; edema of the lips, tongue, or uvula; erythema of the periorbital area; conjunctival edema by physical exam);
- Bronchospasm (by symptoms);
- Chills (by subject report after specific query by clinical staff);
- Tachycardia, bradycardia, other dysrhythmias, dyspnea, hypertension, hypotension (by vital sign measurements heart rate, blood pressure, and respiration rate);
- Hemolysis or acute hemolytic transfusion reactions resulting in circulatory/cardiovascular dysfunction (by clinical laboratory result); and
- Infection (by physical exam or clinical laboratory results).

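### As written, subjects are asked about the listed acute reactions on infusion day only in Cohort 3, so symptom-based TEAEs may be found somewhat more completely at the top dose

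*Protocol*

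**What the plan says.** The two infusion sections describe how acute transfusion reactions are to be found.

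- Protocol 8.2.1 (Cohorts 1 and 2; 270 and 540 mL): "Subjects will be observed during and after the study plasma infusion for evidence of acute transfusion reactions".
- Protocol 8.2.2 (Cohort 3; 810 mL of FDP and, at another visit, 810 mL of FFP): "They will be asked about and observed during and after the study plasma infusion for evidence of acute transfusion reactions".

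Both go on to the same list: allergic reactions, heart-rate and rhythm changes, high or low blood pressure, dyspnea, hemolysis, fever, chills, thromboembolic events, bleeding and infection.

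Protocol 10.5.1 sets the general AE method without restricting it to any cohort: "All AEs will be assessed at all study visits, documented in the source records, and recorded on the eCRFs", and "AEs will be assessed using an open-ended question such as" an enquiry about how the subject has been feeling. It adds a focused review of systems and physical exam by the PI or study physician. It also names a way of documenting each kind of infusion reaction, one of which is a direct question: "Chills (by subject report after specific query by clinical staff").

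**The concern.** Conclusions on the safety objectives are to rest only on TEAEs (Synopsis, Objectives; Protocol 6.1), so the way TEAEs are found is the way the primary endpoint is measured. The primary objective is safety at increasing doses. If subjects are questioned about a list of reactions at the highest dose and not at the lower ones, the method of measurement changes together with dose.

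Two uses of the data are exposed:

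- The overall AE and TEAE tables (SAP Tables 2.16-2.20 and 3.10-3.12) put all cohorts in adjacent columns.
- The less prompted cohorts supply the data for escalation. Protocol 6.5 makes each step depend on, among other things, the absence of TEAEs. Under Appendix A the Research Monitor reviews each of the first five subjects in a cohort through the 24-hour visit.

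**Working it through.** No figure in the documents depends on this wording, so the check compares the text.

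**What is the same in all cohorts on infusion day**

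| Element | Cohorts 1 and 2 | Cohort 3 |
|---|---|---|
| Reaction list | 8.2.1 | 8.2.2, same items |
| Stay on site | "Subjects will remain at the study site under direct observation and actively monitored for a minimum of 5 to 6 hours post-infusion" | "Subjects will remain at the study site and be actively monitored under direct observation for a minimum of 5 to 6 hours post-infusion" |
| Vital signs | every 15 min during infusion, every 30 min to 4 h, then every 4 h | same |
| Wells Scale | before infusion; 30 min, 4 h and 24 h after | same |
| Evaluation before release | yes | yes |
| AE assessment at the visit | marked in Tables 4-6 | marked in Table 8 |

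**What differs.** In 8.2.2 subjects are asked about the listed reactions as well as observed. Section 8.2.1 does not mention asking.

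**Does 10.5.1 close the gap?** It names a means of documenting each reaction, for all cohorts:

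- Fever: temperature. Hemolysis: laboratory result. Infection: exam or laboratory result. Heart rate, rhythm and blood pressure: vital signs. These barely depend on asking.
- Chills: a specific query. Covered in every cohort.
- Dyspnea: vital-sign measurements. Mild breathlessness with a normal respiration rate could be missed.
- Allergic reactions, including pruritus: physical exam. Itching without a rash could be missed.
- Bronchospasm: symptoms, with no stated prompt.

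For the last three, Cohorts 1 and 2 have the open-ended question and the physician's review and exam. Cohort 3 has these and is also asked about the listed reactions.

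**Do later contacts close the gap?**

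- The 24-hour visit (8.3.1) reviews AEs since the infusion visit and includes a complete exam, in all cohorts. It can recover infusion-day symptoms, but it does not go through the reaction list.
- The telephone script (Appendix H) uses one symptom checklist for all cohorts. Its prompts ask about the last 24 hours, and the first call is at 48 hours (8.3.2), so they do not reach back to infusion day. The general opening question of the call may.

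**What remains.** A difference in infusion-day questioning, confined to a few symptom-based items.

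**What one subject weighs.** With 8 subjects planned per cohort, one extra subject with a TEAE moves incidence by 1/8 = 12.5 percentage points. In a column for one arm of 4 it moves incidence by 1/4 = 25 points. This shows how coarse the tables are. It does not estimate the effect.

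**The case against.** The strongest reply is that this is near-duplicate text drafted inconsistently, with 10.5.1 as the governing method for everyone. Most listed reactions are found by measurement, exam or laboratory test, and chills are queried in every cohort. Section 8.2.2 contains no checklist, script or times for asking, and some items, such as hemolysis, are not things a subject can usefully be asked about. Section 6.3 sends procedural detail to the Manual of Procedures, so site practice may be identical. All of this stands. It confines the point to a few symptoms and makes it one about the text, not about demonstrated practice.

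It can also be said that no hypothesis is tested (Protocol 11.1, 11.3) and that cohorts of 8 are too small to show a modest difference. The exact 95% interval is 0.3-52.7% for 1 of 8 and 3.2-65.1% for 2 of 8. That is correct, but the DSMB and sponsor will read raw counts, and imprecision is no reason to keep an avoidable systematic difference.

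Finally, the Cohort 3 columns already differ in exposure, because those subjects have two infusions, one of them FFP, and follow-up to Day 43. Aligning the wording will not make the tables a clean dose comparison; it removes one of several differences.

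A reader might infer from 8.2.1 and 8.2.2 alone that lower-dose subjects are merely watched, or that TEAE incidence will rise with dose as an artefact. The documents support neither reading. Section 10.5.1 and the 24-hour visit provide questioning in every cohort, and nothing shows that a gradient would result.

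**Conclusion.** The inconsistency is real and its consequence is limited. As written, infusion-day questioning about the listed reactions applies only at 810 mL. Symptom-based TEAEs such as mild dyspnea, pruritus or bronchospasm could therefore be somewhat more completely captured at the top dose, and somewhat less completely in the cohorts that inform escalation.

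The documents allow no estimate of the size; it is probably small. This conclusion assumes that staff follow 8.2.1 and 8.2.2 literally and that the Manual of Procedures does not already set one procedure for all cohorts. If it does, only the wording needs tidying.

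The Cohort 3 comparison of FDP with FFP is unaffected, since the same wording governs both infusions in the same subjects. Severity is low: this is a nearly free improvement.

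**What to change.** In Protocol 8.2.1, state that subjects are asked about as well as observed for the listed reactions, as 8.2.2 does. Cross-refer both sections to 10.5.1, so that one procedure for eliciting acute reactions applies to every cohort on infusion day. Since 8.2.2 gives no times for asking, the aligned text need not either; if times are wanted, they should be the same in all cohorts.

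The cost is one sentence, a cross-reference and a matching line on the site worksheet. Sample size, tables and analyses do not change. The downside is that a few more mild events may be recorded at the lower doses.
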